### 3.2 END OF STUDY DEFINITION

A Participant is considered to have completed the Study if he/she/they have remained a Participant for the entirety of the Study period and have completed the applicable end of Study REDCap Cloud survey. Therefore, up to 14 days for the At-home Phase, including Study intervention, is sufficient time to collect data and evaluate the interventional device. Since Study Sites are required to see all Participants after the At-home Phase, up to 28 days for the In-person Phase is sufficient time to see all Participants as patients through already scheduled visits, overbookings or separate dedicated clinics. Biopsy results typically take 7 days to follow up, however Study Coordinators will continue to monitor EMR of Participants to collect relevant data up to 30 days following the end of the Study.

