Participant Safety	There remains the risk that a Participant may not identify a skin lesion on their body that is malignant (both a PSLC and a non-PSLC). However, all risks are associated with the current at-home standard of care protocol for SSEs and not increased by use of the Sklip System. All Participants are required to come for an in-person FBSE, regardless of if they identify a PSLC during the At-home Phase. The FBSE will ensure that no malignancies are missed.
Synopsis of Statistical Analysis	
An intent-to-treat (ITT) analysis set will include those who are enrolled in the Study regardless of adherence. All primary analyses will be conducted using the intent-to-treat analysis set. Demographic and clinical characteristics will be summarized using descriptive statistics (e.g. proportions, mean/median, and standard deviation/range).
 
The Ground Truth will be the combination of the following:
 
Dataset N) DDI dermoscopic diagnosis ground truth (DDI-GT) for PSLCs that were not biopsied during the In-Person Phase, and

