### 5.6 LOST TO FOLLOW-UP

A Participant will be considered lost to follow-up if the individual fails to submit the REDCap Cloud survey administered at the end of each Phase.

The following actions must be taken if a Participant fails to complete the end of Study survey:

- A Study Coordinator will attempt to contact the Participant and counsel Participant on importance of completing the survey
- Before a Participant is deemed lost to follow-up, the investigator or designee will make every effort to regain contact with the Participant (2 attempts to contact via virtual communication message, text messages, email, or phone call). All contact attempts made by the Study team will be documented in the Participant's medical record or Study file
- Should the Participant continue to be unreachable, he or she will be considered to have withdrawn from the Study with a primary reason of lost to follow-up

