**7.2 DISCONTINUATION FROM STUDY INTERVENTION**

Discontinuation from the Study intervention (reported discontinued use of Sklip System by Participants) does not mean discontinuation from the Study, and remaining Study procedures (nPhase REDCap Cloud survey, chart reviews) should be completed as indicated by the Study protocol.

The data to be collected at the time of Study intervention discontinuation will include the following:

- a) Anonymous Sklip App analytics per Study Participant (frequency of use)
- b) Data obtained from chart reviews to track the number of submitted PSLCs, the number of PSLCs identified as SUSPICIOUS by the dermatology Provider during the in-person FBSE, the chosen method of follow-up, and any relevant pathology results for each Participant.
- c) Data from the end of Study REDCap Cloud survey.

Participants MUST discontinue investigational product for any of the following reasons:

- Participant's request to stop Study intervention. Participants who request to discontinue using the provided Sklip System will remain in the Study and must continue to be followed for protocol specified follow-up procedures. The only exception to this is when a Participant specifically withdraws consent for any further contact (refer to Section 5.2)
- Loss of ability to freely provide consent through imprisonment, or involuntarily incarceration for treatment of either a psychiatric or physical (e.g., infectious disease) illness.

All Participants who discontinue Study intervention should comply with protocol specified follow-up procedures as outlined in Section 8. If Study intervention is discontinued prior to the Participant's completion of the Study, the reason for the discontinuation must be documented in the Participant's medical records and entered on the appropriate CRF.

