## 8.7     **EARLY TERMINATION OR END OF TREATMENT VISIT**

EARLY TERMINATION – N/A; PARTICIPANTS DO NOT HAVE A PHYSICAL STUDY VISIT

END OF TREATMENT – N/A

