## 10. SAFETY

### 10.1 SPECIFICATION OF SAFETY PARAMETERS

The investigational device being assessed in this Study (Sklip System) is not of substantial importance in diagnosing, curing, mitigating, or treating disease. Instead, it provides a triage assessment according to a clinically accepted protocol, which is intended for confirmation by a healthcare professional. Therefore Participants enrolled in the Study are not exposed or introduced to any additional medical safety risks that would warrant scheduled screening assessments. The Participants have the option to be evaluated by a dermatology Provider via standard clinical care pathways, not part of the Study, and would be considered an unscheduled visit (Section 8.9 Unscheduled Visits).

There is minimal risk of psychological or behavioral effects that may be experienced by the Participant during the Study. At the start of enrollment for each Participant, he/she/they will have onboarding training by a Study Coordinator on how to contact a research team member to report any adverse psychological or behavioral effects throughout the duration of their enrollment.

If a Participant reports any adverse events, the investigator will immediately be informed of the event. The investigator will be responsible for assessing the reported adverse events and will be followed by a member of the Study team until resolution/stabilization. The Participant will be offered the voluntary option to withdraw from the Study and discontinue any intervention. The report will be documented in the Participant's record.

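### Completion, loss to follow-up and the contact attempts depend on returning a survey, not on the in-person skin exam that the safety case and the histologic ground truth rely on

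*Combined protocol and SAP*

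**What the plan says.** Completion in Section 3.2 has two parts: the person has "remained a Participant for the entirety of the Study period" and must "have completed the applicable end of Study REDCap Cloud survey". Section 5.6 treats a participant as lost who "fails to submit the REDCap Cloud survey administered at the end of each Phase". The follow-up it lists is counselling about the survey and two contact attempts, and someone who stays unreachable is recorded as withdrawn. The 30-day contact period in the Synopsis (Follow-up Duration) applies to participants lost to follow-up, so it inherits the survey trigger.

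On the exam, the Synopsis (Participant Safety) says "All Participants are required to come for an in-person FBSE" and relies on it so that no malignancy goes undetected. Section 1.3.1 promises it to each participant, and Section 8.1.2 requires it.

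Other sections point the other way. Section 10.1 says "The Participants have the option to be evaluated by a dermatology Provider via standard clinical care pathways, not part of the Study". The early-termination entry in Section 8.7 says "PARTICIPANTS DO NOT HAVE A PHYSICAL STUDY VISIT". Section 8.9 places the exam under unscheduled visits, and the schedule of events in Section 8.10 has no row for it.

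**The concern.** The event that the safety argument and the reference standard both need is attendance at the exam. The event that sets off the written follow-up is survey return. The two can come apart, and then the contact effort goes to the wrong people.

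Non-attendance could plausibly depend on the device output. Section 6.1.1 directs users with a SUSPICIOUS result to in-person consultation. After UNREMARKABLE it suggests self-monitoring, with a consultation if the user does not understand the result or remains worried. A participant without an appointment must contact the site to arrange one, and the visit is billed to insurance or paid by the participant (Synopsis, Medical costs).

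If people with an UNREMARKABLE result attend less often, a falsely reassured participant may go unexamined. False negatives would then lose their histology more often than true positives.

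**Working it through.** **1. What the rules produce, read literally**

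| Participant | Section 3.2 | Section 5.6 |
|---|---|---|
| Stays enrolled, returns survey, no exam | Can count as complete | Not lost; no contact defined |
| Attends exam, does not return survey, unreachable | Not complete | Lost, treated as withdrawn |

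**2. Route to the primary analysis**

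Under Section 11.4.2, true positives and false negatives are both counted only among biopsied lesions with a histologic ground truth (Dataset O). Those biopsies are taken in the in-person phase (Section 3.1), and Section 11.5 rules out imputation. A malignant lesion on a non-attender therefore enters neither count.

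**3. The plan's own sample size, and what extra non-attendance does to it**

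Inputs from Section 11.2: sensitivity 97.4%, prevalence 2.3%, margin 10%, 1.5 lesions per participant, 10% drop-out.

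- Lesions: 1.96² × 0.974 × 0.026 / (0.10² × 0.023) = 422.98, so 423. Reproduced.
- Participants: 423 / 1.5 × 1.10 = 310.2, so 310. Reproduced.
- Without loss: 310 × 1.5 = 465 lesions. Non-attendance above 1 − 423/465 = 9.0% takes the total below 423.
- After 10% drop-out: 310 × 0.90 = 279 participants and 279 × 1.5 = 418.5 lesions.

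Drop-out is not defined by exam attendance, so survey completers without an exam could come on top of the 10%. The documents give no rate; the shares below are assumptions.

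| Share of the 279 who skip the exam | Participants without exam | Lesions with exam | Expected melanomas among them (2.3%) |
|---|---|---|---|
| 5% | 14 | 398 | 9.1 |
| 10% | 28 | 377 | 8.7 |
| 20% | 56 | 335 | 7.7 |

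**4. Bias in sensitivity if attendance depends on output**

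Let a_S and a_U be the proportions of SUSPICIOUS and UNREMARKABLE lesions that reach the exam. Assume that attendance depends only on the output and that every malignant lesion examined is biopsied. Then

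observed Se = Se × a_S / [Se × a_S + (1 − Se) × a_U].

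With a_S = 0.95 and a_U = 0.80 (assumed):

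- True 90%: 0.855 / (0.855 + 0.080) = 91.4%.
- True 80%: 0.760 / (0.760 + 0.160) = 82.6%.

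If a_S = a_U, the attendance terms cancel and there is no bias.

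**5. Are these rates compatible with the plan?**

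On the 257 SUSPICIOUS and 166 UNREMARKABLE lesions in Table 6, the lesions lost are (257 × 0.05 + 166 × 0.20) / 423 = 46.05 / 423 = 10.9%. Taking instead Table 6's 49.0% malignant share with sensitivity 90% and specificity 30%, the UNREMARKABLE share is 0.49 × 0.10 + 0.51 × 0.30 = 0.202, and the loss is 0.798 × 0.05 + 0.202 × 0.20 = 8.0%. Both are close to the planned 10%. With a_U = 0.60 the same two calculations give 18.7% and 12.1%, which exceed it.

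**The case against.** The plan clearly intends people to attend. Section 3.2 itself obliges sites to see everyone, and charts are reviewed every 7 days for requests to begin the in-person phase (Section 3.1). Onboarding states the requirement (Section 6.1.8), and providers accept overbookings (Section 8.9). The end survey asks how many suspicious lesions the provider found, and the schedule of events includes chart review and messages or calls at Day 42. A reader might infer that non-attenders are not pursued, or that nothing could detect them. The documents do not support that: these steps promote attendance and could reveal its absence. What is missing is a written action once it fails.

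Four other strong readings also fail.

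- **The exam is the only safeguard.** It is the main stated one. The output wording also sends SUSPICIOUS and repeated ERROR results to a provider, and invites users with an UNREMARKABLE result to consult if still concerned.
- **Section 7.2 drops the exam for those who stop using the device.** Its text, "remaining Study procedures (nPhase REDCap Cloud survey, chart reviews) should be completed", omits the exam. The same section refers to the follow-up in Section 8, which includes the exam, and collects findings from it. Section 8.7 is likewise loose wording about early termination and weak evidence that the exam is optional.
- **The completion label distorts the analysis.** The intent-to-treat set covers everyone enrolled regardless of adherence, and no analysis uses completer status. Any bias comes from non-attendance itself.
- **Sensitivity could be inflated by much more.** That needs attendance after UNREMARKABLE well below 80%, which exceeds the planned drop-out. Attendance is also a participant-level event: someone with one lesion of each output who attends has both examined, which dilutes the difference.

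It is also fair to say that completion requires remaining in the study throughout, and that Section 5.5 allows discontinuation for significant non-compliance with the intervention. It does not say that a missed exam qualifies. None of this supplies the missing trigger.

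**Conclusion.** The point holds as a gap in the rules combined with a contradiction between sections. Completion, loss to follow-up and the contact attempts are tied to a survey, while the Synopsis and Sections 1.3.1 and 8.1.2 require or promise the exam for all. Section 10.1 calls provider evaluation optional and outside the study, and Sections 8.7, 8.9 and 8.10 do not treat the exam as a scheduled visit. These passages must be reconciled; which rule is right is for the sponsor and investigators.

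The statistical consequence is conditional. Under the assumed 95% versus 80% attendance, the upward bias in sensitivity is about 1.4 points at a true 90% and 2.6 points at a true 80%. It is zero if attendance does not depend on output. The documents give no attendance rates, and the plan includes no report that would show whether the assumption holds. The change should be made because existing contact effort is attached to the wrong event and correcting that is cheap.

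**What to change.** 1. Reconcile the Synopsis (Participant Safety) and Sections 1.3.1, 3.2, 5.6, 8.1.2, 8.7, 8.9, 8.10 and 10.1 on the status of the exam.
2. Record exam attendance separately from survey return.
3. If the exam is confirmed as required, attach the existing contact attempts and a flag from the 7-day chart review to exam attendance as well as to the survey, and show the exam in the schedule of events.
4. In either case, report exam attendance and availability of ground truth by SMSA output (SUSPICIOUS, UNREMARKABLE, ERROR), so that differential loss can be seen.

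The cost is protocol wording and one tracking field; the contact attempts and chart reviews are already planned. The reported completion rate may fall if participants who return only the survey no longer count as complete.

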### 3.3 STUDY DISCONTINUATION AND CLOSURE

This Study may be temporarily suspended or prematurely terminated if there is sufficient reasonable cause. Written notification that documents the reason for Study suspension or termination will be provided by the suspending or terminating party to OHSU Coordinating Center, local IRB, and other regulatory authority. If the Study is prematurely terminated or suspended, the Investigator will promptly inform the IRB and provide the reason for the termination or suspension.

Reasons for terminating the Study may include the following:

- Unfavorable assessment of risk/benefit ratio
- Incidence or severity of adverse events, in this or other studies, that indicates a potential health hazard to Participants

- Demonstration of efficacy that would warrant stopping
- Data that are not sufficiently complete and/or evaluable
- Investigator not adhering to the Study protocol or applicable regulatory guidelines in conducting the Study
- Participant enrollment is unsatisfactory
- Submission of knowingly false information from the Study Site to OHSU Coordinating Center or regulatory authority
- Upon instruction by local or other regulatory or oversight authority.

The Study may resume once concerns about safety, protocol compliance, and/or data quality are addressed as applicable and requirements of the OHSU Coordinating Center, Study sponsor, IRB and/or other applicable regulatory authority are satisfied.

## 4. STUDY POPULATION

### 4.1 PARTICIPANT INCLUSION CRITERIA

To be eligible to participate in this Study, an individual must meet all of the following criteria:

1. Participant must provide written informed consent before any Study-specific procedures or interventions are performed.
2. Age  $\geq 21$  years with at least one pigmented skin lesion (PSL)/mole on their body. All genders and members of all races and ethnic groups will be included.
3. Participant self-identifies as having Fitzpatrick Skin Type 1 through 4.
4. Participant must be a current or new patient through self-referral or Provider-referral at the participating Study Site.
5. Participant must have access to a smartphone/tablet and be willing to set up virtual communication via direct message to a Study Site dermatology provider (i.e. MyChart in EPIC, direct message in ModMed EMA or other electronic medical record (EMR) type)
6. Participant must be English-speaking due to FDA Breakthrough Designation of the Sklip System in the English language. Therefore, we are unable to accommodate non-English speaking Participants.
7. Participant must be “Healthy”, which is defined as someone considered not urgently sick or hospitalized. This will be determined by the Study principle investigator (PI) at each Study Site, a licensed dermatologist, who will be responsible for screening Participants to ensure eligibility criteria is met prior to enrollment.

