## 5.3 MEASURES TO MINIMIZE BIAS

### 5.3.1 RANDOMIZATION/MASKING PROCEDURES

Blinding is considered unnecessary to reduce bias for all the observations because follow up evaluation for all Participants will follow standard clinical care pathways and is not affected by this interventional Study. The Study Site PIs and DPs will be fully blinded to all results of the At-home Phase, including the Participant Mole Log Sheet. Participants will be informed of the blinding activity prior to their FBSE to avoid DP selection-bias. Specifically, the dermatology provider will be instructed to say the following to each participant upon entering the patient room for the in-person FBSE: "Hello, my name is [name and title], the purpose of today's visit is to complete a full body skin examination as part of the at-home dermatoscopy study. To avoid bias, please hold with any questions related to your moles of concern until I have verified that I completed your full body skin examination and all other study related activities. I will be happy to address your questions or concerns at that time."

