#### **What should you do?**

- a) **Consult** this result in person with your established local healthcare provider, or

b) **Consult** this result in person with a dermatology provider by searching your geographic location within the Sklip network map. Click the **TAKE ACTION** button in this result to find a local dermatology office in the Sklip map.

c) **Consult** this result in person and **get a prioritized office visit within 14 days without the need for a referral**. Click the **TAKE ACTION** button in this result to find local dermatology offices in your area. Then click the **SKLIP NETWORK** filter button to identify a Sklip verified dermatology office.

*Costs associated with consulting your mole scan result with a healthcare provider are your financial responsibility and Sklip is not responsible for costs associated with medical care or verifying insurance coverage”*

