#### 8.1.2 DISEASE ASSESSMENT

All Participants will be required to obtain an in-person FBSE. Since PSLCs will be evaluated per standard clinical care pathways, the evaluating dermatology Provider may or may not be involved in the Study. The dermatology Provider will be blinded to Participant activity, including the Participant Mole Log Sheet. The dermatology Provider may choose to perform biopsy, when applicable, independent of Participant at-home findings.

Biopsies may be performed for suspicious lesions identified by the dermatology Provider during the FBSE and will be assessed by histologic assessment as part of current standards of care for diagnosis, independent of the Study. **The use of the Sklip System is for triage only and is not intended to act as a substitute for official diagnosis via pathology results, and all subsequent management and treatment of disease will be based off official histologic diagnosis and in accordance current guidelines.**

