## 8.6 ASSESSMENTS DURING TREATMENT

Not applicable. There is no interventional treatment or therapies in this Study. The number of submitted PSLCs, the number of PSLCs qualified for follow-up, the chosen method of follow-up, and any relevant pathology results for each Participant will be recorded and analyzed as part of period retrospective chart reviews conducted by a Study Coordinator as described in Sections above.

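### The examiner is called fully blinded to at-home results, but EMR messaging and the chart are left as an unprotected route; closing it is a cheap improvement

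*Combined protocol and SAP*

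**What the plan says.** **Blinding.** The Synopsis and Section 5.3.1 state that site investigators and dermatology providers "will be fully blinded to all results of the At-home Phase, including the Participant Mole Log Sheet". Section 8.1.2 repeats the blinding for the examining provider, but also says that "the evaluating dermatology Provider may or may not be involved in the Study".

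**Messaging.** Section 4.1 item 5 requires a participant to "be willing to set up virtual communication via direct message to a Study Site dermatology provider". The channel is the medical record system: "i.e. MyChart in EPIC, direct message in ModMed EMA or other electronic medical record (EMR) type".

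**Where submitted lesions are counted.** Section 8.6 lists "The number of submitted PSLCs, the number of PSLCs qualified for follow-up, the chosen method of follow-up" and pathology results as items that "will be recorded and analyzed as part of period retrospective chart reviews conducted by a Study Coordinator". Section 7.2, for participants who stop using the device, lists "Data obtained from chart reviews to track the number of submitted PSLCs". By contrast, Section 3.1 (schedule for data collection, Dataset A) has the coordinator record the at-home count in REDCap Cloud, guided by the mole log and the participant's images. Section 6.1.8 sends a copy of the log by REDCap upload or email.

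**Safeguards described.** Participants are told about the blinding before the full body exam. The provider reads a script on entering the room (Section 5.3.1). The mole log is handed to the coordinator when the provider is not present (Section 3.1).

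**The concern.** The blinding is stated without qualification, yet eligibility depends on willingness to open a message line to the same group of clinicians, and two sections look for lesion submissions in the chart that an examiner in routine care can open. Section 8.1.1 also lists portal encounters and direct messages among the items to be obtained from the medical record, so the plan itself treats such messages as chart content.

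Two analyses depend on the examiner. In Section 11.4.2, true positives and false negatives for melanoma and atypical nevi are defined on biopsied lesions with histology (Dataset O), and squamous and basal cell carcinoma follow the same approach. The examiner's decision to biopsy therefore determines which lesions enter sensitivity. In Section 11.4.3, the provider's lesion count is one of the two counts compared in exploratory endpoint 4. If at-home findings reached the examiner beforehand, either could shift. If messages were sent more often for SUSPICIOUS lesions, biopsy would become linked to the index test and apparent sensitivity would rise.

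**Working it through.** The point rests on text, so the check is to trace each route by which at-home information could reach the examiner and see whether a safeguard covers it.

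| Route | Text | Covered? |
|---|---|---|
| Conversation in the exam room | Script, Section 5.3.1 | Yes |
| Mole log | Given to the coordinator without the provider (3.1); copy by REDCap or email (6.1.8) | Yes |
| Message before the visit | Channel required by 4.1 item 5; content not limited, not routed away from the examiner | No |
| Chart opened before the exam | 7.2 and 8.6 name the chart as the source of submitted lesions; viewing not restricted | No |
| Record of any exposure | No field described | No |

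Is lesion content expected on the uncovered routes? The thirteen at-home steps in Section 3.1 send no lesion, image or algorithm output to a provider; the last step is only to schedule the visit. The messaging uses described are recruitment and study contact (Section 5.1 and the schedule of events in 8.10). The weekly chart reviews in Section 3.1 track requests to begin the In-person Phase. The routes are therefore open, but no section directs lesion content into them.

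The plan has no figure to reproduce here, and the documents give no rate of messaging or of unprompted biopsy. The following illustration uses **assumed** inputs:

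- true sensitivity Se = 0.90;
- unprompted biopsy probability for a cancer bN = 0.85, or 0.60 as a harsher case;
- a fraction m = 0.2 to 0.4 of SUSPICIOUS cancers is messaged ahead and then always biopsied; no UNREMARKABLE cancer is messaged.

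Biopsy probability for SUSPICIOUS cancers: bP = bN + (1 − bN) × m.

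Observed sensitivity = Se × bP / [Se × bP + (1 − Se) × bN].

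- bN = 0.85, m = 0.2: bP = 0.88; 0.792 / (0.792 + 0.085) = 90.3%.
- bN = 0.85, m = 0.4: bP = 0.91; 0.819 / (0.819 + 0.085) = 90.6%.
- bN = 0.60, m = 0.2: bP = 0.68; 0.612 / (0.612 + 0.060) = 91.1%.
- bN = 0.60, m = 0.4: bP = 0.76; 0.684 / (0.684 + 0.060) = 91.9%.

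For scale, Table 6 expects 10 melanomas and 21 atypical nevi. One lesion of 31 is 1/31 = 3.2 percentage points, more than any of these shifts.

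The same model tests an obvious remedy, repeating the primary table without exposed participants. Assuming one cancer per participant, the exclusion removes the fraction m of SUSPICIOUS cancers and no UNREMARKABLE ones. The remaining cancers are all biopsied at the same rate, so:

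Observed sensitivity = 0.9(1 − m) / [0.9(1 − m) + 0.1].

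- m = 0.2: 0.72 / 0.82 = 87.8%.
- m = 0.4: 0.54 / 0.64 = 84.4%.

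The exclusion is off by −2.2 to −5.6 points, against +0.3 to +0.6 (or +1.1 to +1.9) for the leakage itself.

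**The case against.** The strongest reply is that nothing in the protocol sends lesion information to the examiner. Item 5 asks for willingness to set up messaging, and with a provider at the site, not necessarily the one who examines. Section 7.2 covers only participants who stop the device. Section 8.6 opens as not applicable and refers back to earlier sections, so its chart wording may be no more than a loosely named data source. Section 8.1.2 also says that the provider is blinded and may biopsy independently of at-home findings. All of this stands, and it limits the point to an unprotected route. It does not close the route: none of these passages limits what a participant may write or what the examiner may read before the visit.

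A reader might infer more in three places.

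- *That lesion submissions are expected in the chart the examiner opens.* Sections 7.2 and 8.6 suggest it, but Sections 3.1 and 6.1.8 describe a different flow, and neither 7.2 nor 8.6 says that lesions arrive by message. The sections conflict on the source; they do not show leakage.
- *That the SUSPICIOUS output creates a message route.* It tells the user to consult "this result in person with your established local healthcare provider", which is a visit and not a message. Within the study, the arranged visit is the full body exam, where the script applies. Nor is it established that messages would favour SUSPICIOUS lesions: the UNREMARKABLE text also invites a consultation if the user is still concerned.
- *That any lesion notified in advance inflates agreement in exploratory endpoint 4.* That endpoint compares mean counts by paired t-test and has no agreement measure. Notification changes the provider's count only for a lesion that would otherwise have gone unmarked, and if that count is already the higher one, the difference widens.

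**Conclusion.** The point holds as a cheap improvement. Full blinding is asserted, but the message and chart routes are not protected, and the source of submitted lesions is named inconsistently between Sections 7.2 and 8.6 and Section 3.1. The documents do not show that unblinding is planned or has occurred.

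The size of any effect cannot be derived from the documents. Under the assumed rates above it is +0.3 to +0.6 points of sensitivity, and +1.1 to +1.9 only if examiners would leave 40% of cancers unbiopsied without prompting. Both the upward direction and the size depend on messages favouring SUSPICIOUS lesions and on messaged cancers always being biopsied. The case for acting rests on the role of the biopsy decision in Section 11.4.2 and on the importance the sponsor already gives to examiner blinding: the summary of changes links the script to FDA concerns. Without a record made before each exam, the sponsor could not later show that the blinding held.

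**What to change.** 1. **Section 4.1 item 5:** direct study messaging to the Study Coordinator or a research inbox.
2. **Sections 7.2 and 8.6:** take submitted lesions from REDCap and the mole log, consistent with Dataset A in Section 3.1.
3. **Section 6.1.8:** add to onboarding that study photos and algorithm results go only to the coordinator before the full body exam, while participants stay free to contact any provider about a worry.
4. **Section 8.1.2:** reconcile the statement that the examiner may be outside the study with the marking, script and blinding duties given to that person.
5. **REDCap:** add one field, completed before the exam, on whether the examiner has seen any at-home information. Report its frequency by SMSA output.

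Do not add a repeat of the primary table without exposed participants. Exposure may be linked to the SMSA output, and under the model above that exclusion lowers sensitivity by more than the leakage raises it.

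Cost: wording in five sections and one data field. The downside is that someone must read the coordinator inbox. Because participants may still contact a provider, the route is narrowed rather than sealed, which is why the exposure field is needed.
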